We now have a unique opportunity to study a nutraceutical ketone ester (**KE**), (R)-3-hydroxybutyl (R)-3-hydroxybutyrate (commercially known as "DeltaG"), that provides systemic ketosis in a deep phenotyping study of HFpEF patients.⁹ Initial studies of DeltaG demonstrated significant improvement in exercise capacity among endurance athletes.¹⁰ Because exercise limitation is a cardinal feature of HF, KE therapy has the potential to likewise improve exercise capacity in HFpEF.

Our **Specific Aims** and **Hypotheses** are as follows:

Aim 1. To determine the acute effects of single dose DeltaG administration on maximal (peak VO₂) and submaximal exercise capacity (exercise time) assessed by cardiopulmonary exercise testing (CPET) among patients with HFpEF.

Hypothesis: DeltaG will improve peak VO₂ and submaximal exercise time compared to a matching placebo.

Subaim 1. To determine the impact of DeltaG on metabolic and biomarker profiles during exercise.

Hypothesis: DeltaG will reduce lactate production during exercise.

- Aim 2. To assess the effects of DeltaG on cardiovascular hemodynamics during exercise.

 Hypothesis: DeltaG will reduce systemic vascular resistance as well as demonstrate improvements in cardiac output at peak exercise compared to placebo.
- Aim 3. To profile the effects of ketone ester versus placebo on systemic and plasma carbohydrate metabolism during exercise using indirect calorimetry and stable isotopes (²H-glucose) techniques *Hypothesis: Delta G will reduce systemic carbohydrate utilization at steady-state during submaximal exercise, with concordant reductions in plasma glucose oxidation*

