The study intervention will be administered approximately 1 hour prior to exercise for the maximal incremental protocol. 9, 10 Because of logistical issues, up to 105 minutes after drink consumption will be allowable without deviation. For the submax protocol, we will provide a half-dose of study drug ~30 minutes prior to exercise since it is expected that some of the compound will be in the body still from the max effort CPET. For similar logistical issues, up to 60 minutes will be allowable without deviation. For comparison, website marketing of the commercial drink recommends ingestion 30 minutes prior to athletic performance, with additional dosing every 1.5-2.0 hours (https://hvmn.com/ketone-ester, accessed 12/7/2019).

At the end of Visit 3, the participants will be asked if they knew which arm they were randomized to and how confident they were using a validated blinding assessment tool.⁴³

Cardiopulmonary exercise testing

We will use a supine cycle ergometer along will a metabolic cart to measure expired gases.

Maximal intensity protocol: Subjects will perform a maximal exertion-limited exercise test using a graded-exercise protocol. Resistance will begin at 15 Watts (W) for 3 minutes, increasing to 25W for 3 minutes, then increasing by 25W every 3 minutes thereafter. Vital signs will be monitored during the test.

We will define peak oxygen uptake (VO₂) as the average value during the final 30 seconds of exercise. The gas exchange/ventilatory threshold (VT) will be determined using both the V-slope and

ventilatory equivalent methods, with the results of the two measurements averaged when both are valid. VE/VCO₂ slope will be calculated from the beginning of exercise until exhaustion. The respiratory exchange ratio (RER) will be calculated as the ratio of VCO₂ to VO₂ during the final 30 seconds of exercise. We will model heart rate and VO₂ recovery following exercise.

The primary outcome of the maximal testing study will be difference in peak VO₂ following ketone therapy as compared to the placebo drink. Secondary cardiopulmonary exercise testing endpoints include exercise efficiency (ratio of work performed to oxygen consumed), total work performed, ventilatory threshold, VE/VCO₂ slope, VO₂ and heart rate recovery.

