Submaximal intensity protocol: Resistance will begin with 1 minute of unloaded pedaling followed by a step-increase to 75% of peak workload (or the workload determined at the first visit). Workload will then be held at this intensity until volitional exhaustion or limiting symptoms prevail (e.g. subject cannot continue despite verbal encouragement, or subject is unable to maintain pre-specified pedal cadence despite verbal encouragement). Vital signs will be monitored during the test. We will assess exercise endurance time at 75% peak work rate. We may also assess VO₂ kinetics, including Tau, which is the time needed to reach 63% of the total response amplitude, and describe the rate/slope of VO₂ recovery. We will also assess VO₂ efficiency (total O₂ consumed to total work performed), and the respiratory exchange ratio, amongst other parameters gathered during the exercise tests.

The primary outcome for this submaximal part of the study is the difference in exercise endurance at 75% peak work rate following ketone therapy as compared to placebo.

Electrocardiography

A resting 12-lead ECG and prolonged rhythm strip will be obtained prior to exercise, and will be analyzed for rate, rhythm, intervals, and morphology. Heart rate variability metrics will be computed following KE and following the placebo intervention.

Blood sampling and metabolomic profiling

Standard blood testing is performed at Visit 1 for baseline analysis. This may include a CMP, CBC, NT-proBNP, lipid profile, hemoglobin A1c (approximately 20 mL of blood).

We will draw blood frequently before drug, after drug, and during exercise and recovery for measurements. The lab testing protocols are in **Table 2** with **approximate** times noted for planned lab draws (note: given the multitude of lab draws, missing laboratory draws will not be counted as deviations nor is exact timing required for laboratory draws). At Visit 2 and 3, a tertiary goal of blood sampling is to assess the pharmacokinetic (assess circulating ketone levels resulting from the DeltaG) and pharmacodynamic (assess biologic effects of the DeltaG) impact of DeltaG. BHB will be the primary means of determining therapeutic absorption. We will recreate pharmacokinetic curves including C_{max} (peak serum concentration achieved by drug), T_{max} (time at peak serum concentration), and area under the curve (AUC).

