[figure not shown]

Acute Effects of Exogenous Ketone Ester Administration in Heart Failure

Statistical Analysis Plan

ClinicalTrials.gov Identifier: NCT04633460

Date: February 1st, 2024

[name]

[name], ScD

Study Design: Two-sequence, two-treatment individual-randomized crossover design.

Description of Baseline Characteristics: The demographic and clinical characteristics of the sample will be described overall (intention-to-treat) and by arm using descriptive statistics (means, medians, percentages) with measures of the variation (standard deviation (SD) and interquartile range (IQR)). Graphical procedures will be used to assess distributional assumptions.

Primary Analysis: The primary analysis will regress the difference in outcome for ketone versus placebo on treatment sequence. A Wald test of the intercept will be used for the hypothesis test of a treatment effect. The two co-primary outcomes are:

1. Peak VO_2 during incremental (maximal) exercise testing
2. Time to exhaustion during submaximal exercise testing at 75% peak workload

A type I error rate of 0.05 is pre-specified without correction for multiple comparisons.

Secondary Endpoints: The secondary outcomes will be analyzed using the same model. These are:

1. Percent change in systemic vascular resistance with maximal exercise testing at peak
2. Substrate utilization (reflected by the respiratory exchange ratio) during maximal exercise testing at peak
3. VO_2 efficiency (the ratio of total work performed over oxygen consumed above baseline during exercise, kJ/L of O_2) during submaximal cardiopulmonary exercise testing.

Exploratory Endpoints: Exploratory outcomes will be used to further understand possible mechanisms of action for the change in primary and secondary outcomes, and include several domains:

- (a) Resting echocardiographic data: left ventricular ejection fraction, peak left ventricular global longitudinal strain, e' septal and lateral velocity, E/e' ratio, tricuspid annular planar systolic excursion, and the right ventricular s' velocity.
- (b) Exercise hemodynamic data: Cardiac Output (heart rate x stroke volume), VE/VCO_2 slope, the arteriovenous O_2 content difference (quotient of VO_2 to cardiac output), mean arterial pressure, the vasodilatory reserve, and the mitral E to septal e' ratio assessed at:
 - 25 watts of exercise during incremental study
 - Peak of the incremental study
 - 4 min during the submaximal study
 - Time of exhaustion during the submaximal study

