- (c) Exercise metabolic data:
 - Ventilatory Threshold (using the average of the V-slope method and the Ventilatory Equivalents method, when available)
 - Respiratory Exchange Ratio assessed at:
 - 25W of exercise during incremental study
 - Peak of the incremental study
 - 4 min during the submaximal study
 - Time of exhaustion during the submaximal study
 - Beta-hydroxybutyrate, glucose, lactate, non-esterified fatty acids, insulin, and glucagon assessed at:
 - 25W of exercise during incremental study
 - Peak of the incremental study
 - 4 min during the submaximal study
 - Time of exhaustion during the submaximal study

- Glucose kinetics during the submaximal study in the subgroup who received stable isotopes during the intervention visits:
 - Glucose rate of appearance
 - Glucose rate of disappearance

Safety Endpoint: Presence of exercise-induced arrhythmias (significant atrial or ventricular arrhythmias)

Physiologic Response to the Intervention: In addition to the primary and secondary outcomes, multiple other physiologic endpoints were collected, with some at multiple timepoints within each visit. For some endpoints, not all measurements occurred at regular intervals, and the number of measurements per subject varied. These analyses will be analyzed similarly to the primary endpoints, but with changes to address the repeated measurements within visits. In some cases, the responses can be summarized using a single summary statistic, e.g. the area under a curve (AUC) or the initial slope, while in other cases the individual measurements are of interest. Mixed effects models may be employed to efficiently answer questions related to outcome variables with repeated measurements.

Subgroup analyses:

- Biological sex
- Baseline peak VO_2 indexed to body weight (above versus below median value)
- Diabetic status (No versus Yes)
- Left ventricular ejection fraction above and below 60%¹

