A term for subgroup will be included in the model described above. A Wald-test of significance will be used to compare to the null value. This analysis is equivalent to the interaction analysis used in the analysis of parallel-group designs. Results will be presented graphically in a forest plot. Subgroup analyses are considered exploratory and thus no formal corrections for multiple comparisons will be used. Rather across the two primary outcomes, and with 4 subgroups, the expected number of tests with a p-value less than 0.05 is 0.4 hypothesis tests. More than one test with $p < 0.05$ is suggestive of treatment effect heterogeneity.

Hypothesis generating analysis:

The achieved level of ketone in blood immediately prior to exercise is hypothesized to relate to each of the primary outcomes. This hypothesis will be explored graphically and using linear regression models with stratification by treatment sequence.

Power Calculations for Primary Endpoints:

Peak VO_2 : With 18 subjects (9 per treatment sequence), the study has 91% power to detect a mean difference in peak VO_2 (mL/min/kg) between ketone and placebo of 1 mL/min/kg (effect size=0.83), assuming a standard deviation for the difference of 1.2 mL/min/kg.² The power calculation is based on a paired t-test with a two-sided type I error rate of 0.05.

Submaximal Exercise Endurance: Using the effect size noted in a study examining the impact of inorganic nitrate on submaximal exercise endurance in HFpEF,³ a sample size of 18 participants has 88% power to detect an effect size of 0.78, using a paired t-test with a two-sided type I error rate of 0.05, assuming a correlation of 0.8 between measurements on the same individual.

A total of 21 participants were randomized anticipating loss to follow-up of around 3 participants (14%).

References

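### Do the two co-primary outcomes need a stated rule for combining their results?

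*SAP*

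**What the plan says.** The SAP's Primary Analysis section introduces the pair with "The two co-primary outcomes are" and lists peak VO₂ and submaximal time to exhaustion. Each is analysed by regressing the within-person ketone-minus-placebo difference on sequence and testing the intercept. The section closes: "A type I error rate of 0.05 is pre-specified without correction for multiple comparisons".

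The SAP's Power Calculations section treats the outcomes one at a time. Each has 18 participants and a two-sided 0.05, giving 91% for peak VO₂ and 88% for endurance.

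The protocol's Aim 1 hypothesis mentions both outcomes in one sentence: "DeltaG will improve peak VO₂ and submaximal exercise time compared to a matching placebo". Its Cardiopulmonary exercise testing section assigns one primary outcome to each test. For the maximal test: "The primary outcome of the maximal testing study will be difference in peak VO₂". For the submaximal test: "The primary outcome for this submaximal part of the study is the difference in exercise endurance at 75% peak work rate".

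No sentence in either document defines overall trial success or says how to read a split result.

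**The concern.** Two primary tests at an uncorrected 0.05 raise the question of what the trial claims when only one succeeds. Three rules are conceivable: both must be significant, either is enough, or each answers its own question. The word co-primary and the joint hypothesis in Aim 1 lean towards the first. The separate primary outcomes in the protocol lean towards the third. The SAP does not expressly exclude the second.

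The silence is noticeable because the SAP does offer a guide for its eight exploratory subgroup tests: "More than one test with $p < 0.05$ is suggestive of treatment effect heterogeneity". The SAP also describes randomization as done and reports that "multiple other physiologic endpoints were collected, with some at multiple timepoints within each visit", so the matter was still open late in the study. If the choice were made after seeing the results, a split could be presented as support for ketone therapy or as a failure to support it. The protocol's Clinical Significance section says a benefit would be proof of concept for larger trials, so the wording of the conclusion matters.

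**Working it through.** **Inputs.** From the SAP's Power Calculations section: n = 18; two-sided 0.05; paired t-test; peak VO₂ difference 1 mL/min/kg with SD of the difference 1.2, so effect size 1/1.2 = 0.833; endurance effect size 0.78. The correlation between the two outcomes' treatment differences is not given. I assume 0 to 0.8. The 0.8 in the SAP's endurance calculation is between repeated measurements of one outcome and does not supply it.

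**1. The plan's own powers.** The noncentrality is effect size × √18, with 17 degrees of freedom.
- Peak VO₂: 0.833 × 4.243 = 3.54, power 0.9146 (plan: 91%).
- Endurance: 0.78 × 4.243 = 3.31, power 0.8765 (plan: 88%). This takes 0.78 as the mean difference over the SD of the differences.

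With 16 degrees of freedom, as in the model with a sequence term, the powers are 0.9125 and 0.8739. Both stated figures reproduce.

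**2. How often a split occurs at the planned effects.** For independent outcomes:

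0.9146 × (1 − 0.8765) + 0.8765 × (1 − 0.9146) = 0.113 + 0.075 = 0.188.

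Simulation with correlated differences gives 0.146 at correlation 0.5 and 0.098 at 0.8. Over a wider span of correlations, from −0.9 to nearly 1, the figure runs from about 21% down to about 4%. If all 21 randomized participants were evaluable, it would be about 12% at correlation 0 and 6% at 0.8.

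**3. How often a split occurs if only one outcome responds.** For independent outcomes:
- Only peak VO₂ responds: 0.9146 × 0.95 + 0.0854 × 0.05 = 0.873.
- Only endurance responds: 0.8765 × 0.95 + 0.1235 × 0.05 = 0.839.

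Over correlations 0 to 0.8 these run to about 0.89 and 0.86. They are large because they are essentially the power of the one responding endpoint multiplied by 0.95. A split is the correct result in that situation.

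**4. What each reading does to the error rate and power.**

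| Reading | False-positive rate | Power at planned effects, correlation 0 to 0.8 |
|---|---|---|
| Separate questions | 0.05 per question | 91% and 88%, as stated |
| Both required | at most 0.05, no correction needed | 0.9146 × 0.8765 = 80% at 0; 82% at 0.5; 85% at 0.8 |
| Either suffices | neither responds: 1 − 0.95² = 9.75% at 0; about 9% at 0.5; about 8% at 0.8 | 99% falling to 94% |

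Only the third row departs from what the SAP states.

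**5. Which reading the text supports.**
- *Separate questions.* Each exercise test has its own primary outcome in the protocol. Each outcome has its own power statement at 0.05. The SAP's hypothesis-generating analysis relates ketone level to each primary outcome in turn. Aim 1 itself is to determine effects on two capacities. An openly uncorrected 0.05 fits all of this.
- *Both required.* This rests on the label co-primary and on one conjunction. Aims 2 and 3 also combine two results in one hypothesis (vascular resistance and cardiac output; systemic carbohydrate use and plasma glucose oxidation), so this is how the authors phrase hypotheses and not a testing rule.
- *Either suffices.* No sentence says so. It is only not ruled out.

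**The case for a change.** The best argument for a change is that a rule costs one sentence and removes a choice that could otherwise be made with the results in hand. The SAP's authors saw the value of a reading guide for exploratory subgroups, so leaving the primary tests without one is hard to justify. A split is also plausible: the outcomes come from an incremental and a constant-load test, and the second always follows the first.

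Part of this stands. The documents are silent, and a report that claimed overall benefit from one significant outcome would go beyond what the plan supports.

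The rest carries less weight. Both outcomes were already primary in the protocol version dated 1/15/23, before the SAP of February 1st, 2024, so neither was chosen late. Past-tense wording about randomization and collection does not show that results were known, and the documents do not say whether data were unblinded. Both primary results are due under the same model, so a reader will see both and can judge a split directly. The subgroup guide is a rule of thumb for eight exploratory tests (2 outcomes × 4 subgroups × 0.05 = 0.4 expected by chance). It also shows that the authors considered multiplicity and chose openly not to correct.

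**Conclusion.** The gap is one that analysts fill sensibly. Read as two separate questions, which the text favours, the plan gives two sound tests, each at 0.05, with powers of 91% and 88% that reproduce. Requiring both would need no correction, and joint power would be about 80% to 85%. The family-wise error of up to 9.75% arises only if either outcome alone were taken to prove overall benefit, a rule the documents nowhere adopt.

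The 10% to 19% chance of a split at the planned effects depends on 18 evaluable participants and an assumed between-outcome correlation of 0 to 0.8. The 84% to 89% chance when one outcome responds hardly depends on the correlation, but it mainly restates single-endpoint power. Neither figure measures an error in the analysis.

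A sentence saying that the two outcomes are separate questions and are reported together would be a harmless clarification. It would change no endpoint, test, significance level, sample size or estimate, so the plan can stand as written.

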- hypertension, peripheral artery disease, atrial fibrillation or flutter, dyslipidemia, implanted cardioverter-defibrillator, pacemaker, hypothyroidism, diabetes mellitus, and others.
- 5. Vital signs and anthropomorphic measures, including: height, weight, waist circumference, heart rate, systolic blood pressure, diastolic blood pressure, oxygen saturation, and others
- 6. Quality of life, assessed using a validated tool (Kansas City Cardiomyopathy Questionairre)³⁹
- 7. Medications will be obtained from the medical chart and confirmed with the participant.

[figure not shown]
Overall structure of Exercise Visits (visits 1-3)

Figure 1. Flow Diagram of CPET Study Visit Days

[figure not shown]
Baseline Visit 1

Visits 2 and 3 without Isotope Infusion

Visits 2 and 3 with Isotope Infusion

Times and number of blood draws are approximate and only for illustrative purposes

Partipants first come for a baseline visit (**Figure 1**) during which they will undergo cardiopulmonary stress testing in order to determine ~75% of peak work rate. This will allow us to determine the workload for submaximal testing (**Table 1**). We will also perform baseline echocardiography at this visit.

Rationale for selection of exercise tolerance 75% peak work rate and titration procedure: We aim to target a workload that resembles the workload experienced by subjects during routine daily activities, increasing clinical applicability. Selecting too low of a workload, however, could lead to subjects stopping exercise prematurely due to mental fatigue, as opposed to the physiologic processes we seek to modify. Given this, we will perform a familiarization exercise test at ~75% peak work rate during the baseline visit, following the maximal effort study, and modify our submaximal exercise workload based on the subject's performance. We will titrate the workload to target a time to exhaustion of ~3-6 minutes, as longer tests may be limited by boredom or discomfort as opposed to a physiologic limitation. Subjects will begin with a 1 minute period of exercise at 0W, followed by a step increase to 75% peak workload performed until exhaustion. If the subject exercises for >6 minutes, the workload to be used in subsequent studies will be increased by 10W or 15%, whichever is greater; if the exercise time is <3 minutes, the workload will be reduced by 10W or 15%, whichever is less.

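### Secondary endpoint 3 (VO₂ efficiency) is confounded with test duration, itself a co-primary outcome, and is usually biased downward when endurance improves

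*SAP*

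**What the plan says.** The SAP (Secondary Endpoints, item 3) defines VO₂ efficiency on the submaximal test as "the ratio of total work performed over oxygen consumed above baseline during exercise", in kJ per litre of oxygen. It does not say whether baseline is rest or unloaded pedalling, or whether the unloaded minute counts. It gives no time window beyond the exercise itself. Secondary outcomes use the primary model: the ketone-minus-placebo difference regressed on sequence, with no term for test duration.

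The protocol (section 5, Submaximal intensity protocol) describes the test: "Resistance will begin with 1 minute of unloaded pedaling followed by a step-increase to 75% of peak workload". It continues: "Workload will then be held at this intensity until volitional exhaustion or limiting symptoms prevail". On duration, the rationale for the 75% work rate says: "We will titrate the workload to target a time to exhaustion of ~3-6 minutes". The same test supplies the second co-primary outcome, "Time to exhaustion during submaximal exercise testing at 75% peak workload", which Aim 1 hypothesises that the ketone will improve.

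Two further places in the submaximal section matter. It plans to assess VO₂ kinetics, "including Tau, which is the time needed to reach 63% of the total response amplitude", so it recognises that uptake lags a work step. It also describes the efficiency measure the other way up and without subtracting a baseline: "We will also assess VO₂ efficiency (total O₂ consumed to total work performed".

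**The concern.** At constant load, total work is proportional to time. Oxygen uptake starts low after the step and rises towards its plateau, so early work is done with relatively little measured oxygen. In a test of a few minutes this onset deficit is a sizeable share of the total. As the test lengthens, the deficit is spread over more work and the ratio of work to oxygen drifts down. A participant who lasts longer on one drink is therefore compared with themselves over two different durations, and the ratio moves even if metabolism is identical.

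The factor driving this is not random noise. It is an outcome the treatment is expected to change, and randomising the order does not remove it. At stake is the reading of a named secondary endpoint: a true efficiency gain could be reduced or hidden, or a loss reported where none exists. If the ketone shortened endurance, the pull would usually go the other way.

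**Working it through.** **What the plan gives.** There is no expected value, effect or SD for efficiency, so no figure of the plan's can be reproduced for this endpoint. (The endurance power of 88% does reproduce, at 87.6%, and this point does not affect it.)

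**Inputs from the documents.** Constant load to exhaustion; 1 minute at 0 W first; target duration 3-6 minutes, so 4.5 minutes (270 s) is taken as the starting point.

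**Assumptions not in the documents.** Mono-exponential uptake with time constant τ of 30-90 s; A = 10 mL/min per watt; workload P of 20-75 W; unloaded oxygen cost U of 0-0.4 L/min; endurance gain of 10-30%; no true change in steady-state oxygen cost.

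**Baseline = unloaded pedalling.** Let g(T) = T − τ(1 − exp(−T/τ)). Work is P·T, oxygen above baseline is A·g(T)/60 (T in seconds, A in L/min), and efficiency is their quotient. P and A cancel in the percentage change.

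Example with τ = 60 s, 50 W (A = 0.5 L/min) and a 20% gain:
- At 270 s: g = 270 − 60(1 − e^−4.5) = 210.7 s. Work is 13.5 kJ, oxygen 1.756 L, ratio 7.69 kJ/L.
- At 324 s: g = 324 − 60(1 − e^−5.4) = 264.3 s. Work is 16.2 kJ, oxygen 2.202 L, ratio 7.36 kJ/L.
- Change: −4.3%.

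**Baseline = rest, 0 W minute counted.** Oxygen becomes A·g(T)/60 + U·g(T + 60)/60, with the same τ for both parts.

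Percentage change in the ratio, starting from 270 s:

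| τ (s) | +10%, unloaded baseline | +20%, unloaded baseline | +30%, unloaded baseline | +20%, resting baseline (50 W, U = 0.2 L/min) |
|---|---|---|---|---|
| 30 | −1.12 | −2.04 | −2.80 | −0.83 |
| 45 | −1.76 | −3.19 | −4.37 | −1.85 |
| 60 | −2.40 | −4.34 | −5.94 | −2.89 |
| 90 | −3.51 | −6.38 | −8.75 | −4.76 |

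**When the sign changes.** With the resting baseline, dropping the small exponential terms gives oxygen ≈ [(A + U)T − (A·τ − U(60 − τ))]/60. The ratio falls with T only if A·τ > U(60 − τ), because the 0 W minute uses oxygen without doing work and is itself diluted by a longer test. At τ = 30 s the condition is A > U. For a 20% gain at that τ, the change is 0.0% at 20 W with U = 0.2 L/min, 0.0% at 30 W with U = 0.3 L/min, and +0.4% at 20 W with U = 0.3 L/min. At τ of 60 s or more under this model the condition always holds.

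**Against a true benefit (unloaded baseline, 20% gain).** A true fall in oxygen cost of 2.0% (τ = 30 s) to 6.4% (τ = 90 s) is exactly cancelled. A true 5% fall should raise the ratio by 1/0.95 − 1 = 5.3%. It would instead show as +3.1%, +1.9%, +0.7% or −1.5% at τ = 30, 45, 60 or 90 s.

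**Chance of a significant artefact.** Take n = 18, a two-sided paired t-test at 0.05, a 20% gain, no true change and the unloaded baseline. The SD of the paired difference is assumed:

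| SD | τ = 30 s | τ = 60 s | τ = 90 s |
|---|---|---|---|
| 5% | 37% | 93% | >99% |
| 10% | 13% | 41% | 72% |
| 15% | 8% | 21% | 40% |

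**Matched window.** Over an identical window at both visits, duration alone changes the ratio by 0%. Kinetics still matter: if τ falls from 60 to 50 s over a fixed 180 s, g rises from 123.0 to 131.4 s and the ratio falls 6.4% with steady-state cost unchanged.

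**The case against.** Four points can fairly be made against the concern.

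- **The effect is a pull, not an outcome.** A reader might infer that any endurance gain must appear as worse efficiency. The documents do not support that: a true cost reduction of a few per cent offsets or outweighs the pull, and with a resting baseline, low load and short time constant the pull vanishes or slightly reverses. The protocol's incremental test starts at 15 W and then 25 W, so low submaximal loads are possible, though no workloads are given. This stands and limits the claim.
- **The size is assumed.** Time constant, workload, oxygen cost and the meaning of baseline are all unstated. It is also tempting to quote the fall from 3 to 6 minutes, which is 9.0% to 24.8% with the unloaded baseline. That doubles a participant's endurance, and the 3-6 minute range is a titration target, not an expected treatment effect. This stands too.
- **The whole-test ratio is a legitimate prespecified quantity.** It can be computed and described. What it cannot do, without a common window, is separate a change in oxygen cost from a change in duration, and the SAP lists no other submaximal efficiency measure.
- **A matched window does not isolate metabolic efficiency.** It still contains the onset transient, so a treatment effect on kinetics would move it. This is correct, and is why Tau should be reported alongside.

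**Conclusion.** The point holds in limited form. As written, secondary endpoint 3 is confounded with the duration of the test from which it is computed, and duration is a co-primary outcome. Over most of the range examined, longer endurance biases the ratio downward: by about 1-9% for a 10-30% gain from 4.5 minutes with an unloaded-pedalling baseline, and by less with a resting baseline and the 0 W minute counted. In a few cases with a short time constant and low load or high unloaded cost the bias is nil or slightly positive. These sizes rest on an assumed 30-90 s time constant, mono-exponential uptake and, for the resting baseline, assumed workload and unloaded cost. The false-positive rates also rest on an assumed SD.

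The existence of the confounding follows from the test design and does not depend on those figures; its size, and occasionally its sign, do. It can mask a gain or create a spurious loss, but a reversed finding is not certain. Both co-primary outcomes and their power calculations are untouched. The change should be made, but the trial's main conclusions do not depend on it.

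**What to change.** Amend SAP secondary endpoint 3 as follows.

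1. For each participant, compute work and oxygen above baseline at both visits over the same window, from the start of loaded exercise to the shorter of that participant's two exhaustion times. Analyse the ketone-minus-placebo difference on that window with the existing model. The SAP's 4-minute point suits this less well, because tests aimed at 3-6 minutes can end before it.
2. Name the baseline (rest or unloaded pedalling), use the same reference at both visits, and state that the 0 W minute is excluded.
3. Reconcile the SAP ratio with the protocol's inverse, unsubtracted description.
4. Keep the whole-test ratio as descriptive only.
5. Report Tau by treatment beside the matched-window result, so that a change in kinetics is not read as a change in oxygen cost.

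The cost is SAP wording and reprocessing of gas-exchange data the test already records, with no new procedure. The downside is that oxygen data after the shorter exhaustion time are not used for this endpoint. Since the SAP speaks of participants as already randomised, the amendment should be dated and should say whether it preceded unblinding.
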